12 POWER AND SAMPLE SIZE

For this pilot study, the importance of sample size lies in establishing feasibility and the precision of estimated changes which will inform the design of future studies. We will recruit 25 participants at each of four clinics (2 clinics for each intervention), for a total of 50 per intervention, or 40 per intervention allowing for 20% attrition. The clustering of patients within practices, as measured by the intra-class correlation (ICC) may result in a reduced effective sample size. In considering the impact of the ICC, we relied on the ENCOURAGE study⁴⁹, our previous practice-randomized trial of diabetics in the Black Belt. ICCs were essentially negligible in that study; estimated ICCs were <0.01 and not statistically significant. The impact of the ICC is quantified by a design factor (D) defined as $1+ICC \times (N-1)$ where N is the number of subjects per cluster. However, with an ICC of 0.01, the effective sample sizes per group are 40 (without attrition, D=1.24) and 33 (allowing for 20% attrition, D=1.19). This range of sample sizes will allow us to use to estimate changes in body weight with 95% confidence intervals that are ± 0.28 standard deviations to ± 0.35 standard deviations.

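### Section 12: the ±0.28 SD half-width belongs to 50 per arm with no clustering adjustment; the effective size of 40 it appears to describe gives ±0.32 SD

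*Combined protocol and SAP*

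**What the plan says.** Section 12 (Power and Sample Size) justifies the pilot's size by precision, not power: "the importance of sample size lies in establishing feasibility and the precision of estimated changes". It plans 25 participants at each of four clinics, two clinics per arm, "for a total of 50 per intervention, or 40 per intervention allowing for 20% attrition". It then turns to clustering. An earlier practice-randomized trial by the same group is cited as reassurance: "ICCs were essentially negligible in that study; estimated ICCs were <0.01 and not statistically significant". The design factor is defined as D = 1 + ICC × (N − 1), with N the number of subjects per cluster. At an ICC of 0.01, "the effective sample sizes per group are 40 (without attrition, D=1.24) and 33 (allowing for 20% attrition, D=1.19").

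The next sentence opens "This range of sample sizes will allow us to use to estimate changes in body weight"; its claim is that these sizes will serve to "estimate changes in body weight with 95% confidence intervals that are ± 0.28 standard deviations to ± 0.35 standard deviations".

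**The concern.** The sizes immediately before the precision sentence are the effective sizes 40 and 33, so a reader attaches ±0.28 SD to 40 and ±0.35 SD to 33. A half-width for a mean scales roughly with 1/√n, so going from 33 to 40 should shrink 0.35 only to about 0.35 × √(33/40) = 0.32. A fall to 0.28 is too large, which suggests that the lower end omits the clustering adjustment the paragraph has just made.

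This sentence is the only quantitative precision statement in a section with no power calculation. Section 12 also says that the estimates are to inform the design of later studies. If the better-case figure is taken as already corrected for clustering, the precision available from this pilot looks better than the plan's own inputs allow.

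**Working it through.** **Inputs, all from section 12.** 25 per clinic and two clinics per arm, so 50 per arm; 20% attrition, so 20 per clinic and 40 per arm; ICC 0.01; 95% two-sided interval; result in SD units.

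**Step 1: the plan's effective sizes.**
- No attrition: D = 1 + 0.01 × 24 = 1.24; 50/1.24 = 40.3, printed as 40.
- 20% attrition: D = 1 + 0.01 × 19 = 1.19; 40/1.19 = 33.6, printed as 33.

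Both reproduce (33.6 has been truncated).

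**Step 2: half-widths.** For a mean change within one arm, the 95% half-width in SD units is t(0.975, n−1)/√n. With z in place of t it is 1.96/√n.

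| n per arm | Basis | t formula | z formula |
|---|---|---|---|
| 33 | effective, ICC 0.01, 20% attrition | 0.3546 | 0.341 |
| 40 | effective, ICC 0.01, no attrition | 0.3198 | 0.310 |
| 50 | raw, ICC 0, no attrition | 0.2842 | 0.277 |

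The t formula reproduces the printed 0.35 at n = 33; z gives 0.34 there. At n = 40 the t formula gives 0.32. It gives the printed 0.28 at n = 50. By t, the whole numbers that round to 0.28 are 50 to 53, and those that round to 0.32 are 39 to 41.

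**Step 3: other formulas at n = 40.** None gives 0.28.
- Unrounded effective n of 40.3: 0.318.
- t with pooled degrees of freedom (2n − 2): 0.315.
- Difference between arms: 0.438 by z, 0.445 by t.
- 90% z interval: 0.260 (and 0.286 at n = 33, so it fits neither end).
- Degrees of freedom from the number of clinics: 0.68 or more.

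**Step 4: like-for-like ranges by t, no attrition to 20% attrition.**
- ICC 0 (n = 50 to 40): ±0.28 to ±0.32 SD.
- ICC 0.01 (n = 40.3 to 33.6): ±0.32 to ±0.35 SD.

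The printed range takes its lower end from the first line and its upper end from the second.

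**Step 5: sensitivity to the ICC.** With 25 per clinic and no attrition, an ICC of 0.005 (an illustrative value, half the plan's) gives D = 1 + 0.005 × 24 = 1.12, n = 50/1.12 = 44.6 and a half-width of 0.302. The half-width rounds to 0.28 only for n of at least 49.73, that is, for an ICC up to (50/49.73 − 1)/24 ≈ 0.0002. That limit is a rounding cut-off; its use is to show that 0.28 is in effect the ICC-zero value.

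**The case against.** The best defence is that both printed figures are correct for a range that the authors did not label. The paragraph starts at 50 per arm, calls the earlier ICCs negligible, says that clustering may reduce the effective size, and only then works through ICC 0.01. Read that way, the range runs from a best case (50, no clustering, no attrition) to a worst case (33), and one formula reproduces both ends. An arithmetic slip would be unlikely to land on the paragraph's own starting number. On this reading the wording is at fault, not the arithmetic.

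That reading is plausible and cannot be excluded. It does not leave the sentence sound: neither 50 nor an ICC of zero is named as an endpoint, and the sentence follows directly on 40 and 33.

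Two further points stand. First, nothing in the trial depends on the lower figure. Second, all the half-widths above, including the ±0.35 that reproduces, use patient-level degrees of freedom, whereas section 13 (Data Analysis Plan) fits practice as a random effect with only two practices per arm. Reproducing ±0.35 therefore confirms the plan's arithmetic, not that the planned model will achieve that precision.

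**Conclusion.** The concern holds and is minor. As written, the precision range is either wrong at one end or mislabelled. For the effective sizes that the sentence follows, the range should be ±0.32 to ±0.35 SD; the printed ±0.28 needs 50 per arm with no clustering. The better-case half-width is understated by 0.320 − 0.284 = 0.036, about 0.04 SD. In sample-size terms, (0.3198/0.2842)² = 1.27, so the gap is about the size of the clustering adjustment itself (D = 1.24).

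The conclusion rests on reading the figure as a within-arm half-width by the t formula, the reading that reproduces both printed values (at 33 and at 50). The ±0.35 end, the design factors and the planned enrolment are unaffected.

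**What to change.** Change one sentence in section 12, in one of two ways:

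- **Correct the figure:** give the range as ±0.32 to ±0.35 SD for effective sizes of 40 and 33 per arm at ICC 0.01.
- **Label the endpoints:** keep ±0.28 to ±0.35 SD, and say that it runs from 50 per arm with ICC 0 and no attrition to an effective 33 per arm with ICC 0.01 and 20% attrition.

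In either case it would help to say that the figure is a half-width for the mean change within one arm; that is a clarification and not part of the error.

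No more patients, visits or data are needed. The only cost, under the first option, is that the stated better-case precision becomes slightly less favourable.

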13 DATA ANALYSIS PLAN

Mixed models will be used to estimate the changes in outcomes by intervention with confidence intervals using practice as a random effect to account for clustering within practices. Secondary models will adjust for baseline values. In 2011, Katula et al. published 12-month results of randomized controlled trial comparing a community-based translation of a DPP lifestyle intervention conducted in a southern sample with usual care. Combined with data generated in our feasibility trial, this relevant study should further help inform our power assessments for a larger RCT. The change values observed in the control group in that project will serve as a reference for expected change in weight without any intervention and will be used to estimate the change due to the intervention.

Handling of Missing Data

Missing data are expected due to dropouts and missed visits. Weight loss is a subject-level variable and missing assessments would influence tests relative to treatment-by-time interactions. The primary analysis described above will employ restricted maximum likelihood using all data. No patients will be deleted from the analysis because of partial data. To assess the sensitivity of results, weight loss will be

analyzed using: 1) all patients irrespective of missing data to perform analysis of variance using mixed effects multi-level models with repeated measures; 2) only patients who have completed all assessment visits and have no missing data, to perform analysis of variance employing mixed effects multi-level models with repeated measures; 3) all patients, irrespective of missing data, to conduct analyses using mixed effects multi-level time trend models with random coefficients to capture individual time trends (does not require complete data across time); and 4) multiple imputation.

Multiple imputation will be employed to perform statistical inferences that properly account for statistical uncertainty due to missingness. Rubin's multiple imputation procedure replaces each missing value with a set of plausible values that represent the uncertainty about the appropriate value to impute.⁸⁴ Missing values are imputed by drawing random samples, and the process is replicated to provide K data sets with pseudo-complete data. Estimates and corresponding confidence intervals will be plotted against K to determine the optimal K to use in subsequent sensitivity analyses. Mean weight loss is estimated for each data set, and the multiple imputation estimator is the average of the individual estimates. The variance of the estimator is estimated from between- and within-imputation variability. The SAS® procedure PROC MI provides four relevant options for imputation models and will be used in quantifying uncertainty due to missing data.

Statistical summaries will be compiled on the number of patients overall and by arm and who completed study per protocol, did not complete study per protocol, and reasons for not completing. Patient characteristics (age, sex, race, BMI) will be summarized similarly. Multi-level logistic regression will be used to investigate the significance of correlates of failure to complete the study per protocol.

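### The primary model of change omits the baseline value, and all four missing-data sensitivity analyses are written for weight only although HbA1c is also listed as primary

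*Combined protocol and SAP*

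**What the plan says.** Section 13 gives the primary model as follows: "Mixed models will be used to estimate the changes in outcomes by intervention with confidence intervals using practice as a random effect". The next sentence reads "Secondary models will adjust for baseline values", so the primary model is unadjusted.

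The missing-data part of section 13 adds three statements about the primary analysis: "missing assessments would influence tests relative to treatment-by-time interactions"; "The primary analysis described above will employ restricted maximum likelihood using all data"; and "No patients will be deleted from the analysis because of partial data". The sensitivity analyses open with "To assess the sensitivity of results, weight loss will be" and list four: repeated measures on all patients ("all patients irrespective of missing data to perform analysis of variance using mixed effects multi-level models with repeated measures"), the same on patients with complete data, random-coefficient time trends, and multiple imputation. The imputation text names one quantity: "Mean weight loss is estimated for each data set, and the multiple imputation estimator is the average of the individual estimates". HbA1c is not named anywhere in section 13.

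Elsewhere, section 1.1 and section 3 list body weight and HbA1c together as primary outcomes at month 12. Section 7 (Weight) calls weight alone the primary outcome. Weight is measured at baseline, month 6 and month 12. HbA1c is measured by finger-stick at screening, month 6 and month 12 (section 7), so the screening value serves as baseline. Section 12 says that the sample size serves feasibility and the precision of estimated changes.

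**The concern.** With two clinics per arm, randomisation cannot be relied on to balance baseline values. An unadjusted analysis of change carries any baseline difference into the arm difference whenever the slope of follow-up on baseline is not 1. For HbA1c a slope below 1 is likely, because the screening value also decides entry within a narrow range (6.0% to 6.4%) and some regression to the mean follows. A secondary adjusted model will show the corrected figure, but the plan then reports as primary the less precise of two estimates that use the same data.

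The second gap concerns missing data. The plan expects dropout and allows for 20%. For weight, four further analyses would show whether the result depends on how dropout is handled. For HbA1c none is named. The planned logistic regression on non-completion could show who leaves, but not what that does to the estimated HbA1c change. The pilot's estimates are meant to feed the design of a larger trial, so both outcomes need the same treatment.

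**Working it through.** **Yardstick from the plan (section 12).** D = 1 + ICC × (N − 1). With ICC 0.01, D = 1 + 0.01 × 24 = 1.24 and 1 + 0.01 × 19 = 1.19. Effective n = 50/1.24 = 40.3 and 40/1.19 = 33.6, matching the stated 40 and 33. The t-based 95% half-width at 33.6 is 0.351 SD, matching ±0.35. The other limit, ±0.28, matches an undiscounted n of 50 (0.277 with z, 0.284 with t) rather than 40 (0.310 and 0.320). That is a separate matter and is not used here.

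**Baseline adjustment, HbA1c (points).** Assumed, because the documents give no SDs: five equally likely screening values 6.0 to 6.4, so baseline variance 0.02 (SD 0.141); follow-up SD s = 0.3 to 0.4; slope b = 0.3 to 0.8.
- Variance of change: s² + 0.02 × (1 − 2b). Part explained by baseline: 0.02 × (1 − b)².
- s = 0.3, b = 0.3: 0.0098/0.098 = 10%.
- s = 0.4, b = 0.3: 0.0098/0.168 = 5.8%.
- s = 0.3, b = 0.8: 0.0008/0.078 = 1.0%.
- s = 0.4, b = 0.8: 0.0008/0.148 = 0.5%.
- The change SD runs from √0.078 = 0.28 to √0.168 = 0.41.

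**What that means in one trial.** The SE of the baseline arm difference is 0.141 × √(2 × 1.24/50) = 0.0315 points, using the plan's ICC. An imbalance of one SE shifts the unadjusted arm difference by (1 − b) × 0.0315, which is 0.006 points at b = 0.8 and 0.022 at b = 0.3. At s = 0.3, b = 0.3 the SE of the arm difference in change is 0.313 × 0.2227 = 0.070, and (0.022/0.070)² = 0.10. This is the same 10% as above: imbalance protection and variance gain are one quantity, not two. If clinics differ in baseline HbA1c by more than ICC 0.01 implies, the likely imbalance is larger.

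**Baseline adjustment, percent weight change.** Assumed: mean 108 kg, SD 18, 4% mean loss, equal SDs at both times, correlation r. To first order the squared correlation of percent change with baseline is (r − 0.96)²/(1 + 0.96² − 2 × 0.96 × r).
- r = 0.90: 0.0036/0.1936 = 1.9%.
- r = 0.93: 0.0009/0.1360 = 0.7%.
- r = 0.95: 0.0001/0.0976 = 0.1%.
- r = 0.97: 0.0001/0.0592 = 0.2%.

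If the follow-up SD differs from baseline by 5%, the range is about 0.1% to 6%.

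**If practice were the sole random effect.** A month-6 value would then add almost nothing to a missing month-12 value. Assumed: changes in SD units, month-6 to month-12 correlation ρ, logistic dropout with a log-odds slope per SD of month-6 change, 20% total attrition. Bias of a per-arm month-12 change = ρ × mean month-6 change among those seen at month 12.

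| ρ, slope | all dropouts attend month 6 | half leave earlier at random |
|---|---|---|
| 0.5, 0.5 | 0.5 × 0.096 = 0.048 | 0.5 × 0.054 = 0.027 |
| 0.7, 1.0 | 0.7 × 0.173 = 0.121 | 0.7 × 0.100 = 0.070 |
| 0.8, 1.5 | 0.8 × 0.227 = 0.181 | 0.8 × 0.134 = 0.107 |

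Against ±0.35 SD the half-early case is 0.027/0.35 = 8% to 0.107/0.35 = 31% of the half-width, with 95% interval coverage of 94.7% to 90.8%. A model that uses month 6 has bias of at most 0.002 SD in these scenarios. If early leavers are as selective as late ones, it removes only about half (0.05–0.19 falls to 0.03–0.10). With dropout unrelated to month-6 change, the bias is zero.

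**The case against.** A reader might infer that the primary model contains a practice effect and nothing else, and so is biased under outcome-related dropout. The documents do not support that. Section 13 explains the practice effect as a way to handle clustering; it does not call it the only random effect. REML on all data, no deletion for partial data and the remark on treatment-by-time tests make a longitudinal model the likelier reading. Listing repeated measures as sensitivity analysis 1 points somewhat the other way, but that item can also be read as the all-patients counterpart of item 2. The model is incompletely written, not shown to be wrong, and the bias table applies only under the disputed reading and assumed dropout.

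On baseline: adjustment is already planned as secondary, the gain for weight is small, and adjusted per-arm changes refer to a common baseline rather than to the observed arm mean. The last point stands, which is why unadjusted changes should be reported as well. None of this is a reason to keep the less precise model as primary.

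On HbA1c: the primary sentence says outcomes, so HbA1c does receive the main model. The imputation method is described in general terms, and section 7 calls weight the primary outcome. But the sensitivity list and the only stated imputation estimand concern weight loss, and two sections list HbA1c as primary. The gap lies in HbA1c's sensitivity analyses, not in its main analysis.

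**Conclusion.** Two points hold on the text: baseline adjustment is confined to secondary models, and no missing-data sensitivity analysis is named for HbA1c. Both are inexpensive improvements to a pilot's plan rather than faults that invalidate it.

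The gain from adjustment is about 0.5% to 10% of variance for HbA1c change and about 0.1% to 2% for percent weight change, on assumed SDs, slopes and correlations. Chance baseline imbalance is removed from the arm difference as part of that gain.

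The visit and covariance terms need only be stated. It would go too far to say that the planned estimates are biased. Only with practice as the sole random effect would outcome-related dropout after month 6 bias the per-arm month-12 change, by about 0.03 to 0.11 SD with half of dropouts early, or 0.05 to 0.18 SD if all attend month 6. Even then the arm difference is essentially unaffected when dropout acts equally in both arms (0.01 to 0.05 SD at 15% versus 25% attrition with half early).

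**What to change.** - For percent weight change and for HbA1c, make primary a mixed model of the month-6 and month-12 changes with arm, visit, arm-by-visit and baseline value as fixed effects, practice as random effect and unstructured within-patient covariance. State that the screening HbA1c is the baseline value.
- Report the month-12 change per arm and the arm difference. Keep the unadjusted model as secondary and show its per-arm changes beside the adjusted ones.
- Run the same sensitivity analyses for HbA1c, with the month-6 value in the imputation model for both outcomes.
- Report losses before and after month 6 by arm, since month-6 data can inform only the later ones.
- Reconcile section 7 with sections 1.1 and 3 on whether HbA1c is primary.

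The cost is SAP wording and a few model parameters. All values are already collected, and repeated-measures models and multiple imputation are already planned for weight. If a longitudinal primary model was intended, writing out its visit and covariance terms settles that part.

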1 PROTOCOL SUMMARY

1.1 SYNOPSIS

Title:	Preventing Diabetes in the Deep South: Extending Partnerships and Adapting Interventions to Reach Rural Communities at High Risk
Study Description:	Alabama has the 3rd highest rates of diabetes in the United States. The prevalence of diabetes is 14.1% compared with 9.4% nationally; in some areas of the Black Belt, the prevalence is over 20%, or 1 in 5 adults. Roughly 37% of people living in Alabama have pre-diabetes, but only 10% of these individuals know they have it. The Diabetes Prevention Program (DPP) is an evidence-based intensive lifestyle intervention that targeted weight loss and successfully reduced diabetes risk by 58%. However, the DPP was a resource intensive efficacy trial and was not designed to be directly deliverable in real world settings. Community-based adaptations of the Diabetes Prevention Program (DPP) can be feasible but typically fail to show the same benefit as the more intense original trial version of the lifestyle program. The aim of this study is to introduce innovative design elements to a community-based adaptation of the DPP to enhance research effectiveness. To reduce or delay the onset of diabetes among high-risk populations, the American Diabetes Associations recommends taking metformin. "Metformin therapy for prevention of type 2 diabetes should be considered in those with prediabetes, especially for those with $BMI > 30 \text{ kg/m}^2$, those aged < 60 years, and women with prior gestational diabetes mellitus." ¹ We will compare two strategies, lifestyle modification alone versus lifestyle modification plus metformin recommendation, in a group-randomized controlled 2-arm trial.
Objectives:	Conduct a 12-month randomized control trial (RCT) to determine the feasibility of implementing a peer coach-facilitated DPP delivered by telehealth. The DPP will be compared to DPP with metformin therapy recommendations. The goal of the intervention is to prevent or delay the

	Type 2 diabetes among rural primary care patients with pre-diabetes and obesity at high risk for developing diabetes. The primary outcomes are body weight and HbA1c results at month 12. The RCT will test feasibility and provide data that will inform design and power for a future study to assess diabetes prevention as the main outcome measure.
Endpoints:	Percent change in body weight and HbA1c results at month 12

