5 RANDOMIZATION/BLINDING

Randomization. This is a cluster-randomized trial, and enrolled patients at a given clinic will receive the intervention assigned to their clinic. A total of 4 primary care clinics in rural Alabama will be randomized to either 1) Receive lifestyle modification alone (DPP) or 2) Receive lifestyle modification with metformin therapy recommendations (DPP-recommendations).

Blinding. Given that this trial is a small pilot randomized at the clinic level and the interventions are very distinct, patients will know their group assignment, as will clinic staff, CHWs, and research staff that are involved in delivering the intervention.

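### Section 13 plans per-arm changes and never names the month-12 difference between arms, the one estimate that bears on the metformin recommendation

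*Combined protocol and SAP*

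**What the plan says.** The Synopsis states the comparison twice: "We will compare two strategies, lifestyle modification alone versus lifestyle modification plus metformin recommendation, in a group-randomized controlled 2-arm trial", and again "The DPP will be compared to DPP with metformin therapy recommendations". Its endpoints are "Percent change in body weight and HbA1c results at month 12". Section 5 makes the clinic the unit of randomisation: "A total of 4 primary care clinics in rural Alabama will be randomized". Section 12 gives the numbers: "We will recruit 25 participants at each of four clinics (2 clinics for each intervention), for a total of 50 per intervention".

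The analysis text reads differently:

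- Section 13, opening sentence: "Mixed models will be used to estimate the changes in outcomes by intervention with confidence intervals using practice as a random effect". No contrast between arms follows.
- Section 13, same paragraph: the control-group change in an external published trial of a community DPP against usual care is to be the reference for estimating the change that the intervention causes.
- Section 13, missing-data text: the multiple-imputation estimator averages the mean weight loss across imputed data sets. A difference between arms is not mentioned.
- Section 12: the sample is meant to "estimate changes in body weight with 95% confidence intervals" of ±0.28 to ±0.35 SD.
- The only between-arm wording in Section 13 is a remark in the missing-data text that "missing assessments would influence tests relative to treatment-by-time interactions".

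**The concern.** Sections 3 and 6.1 give the DPP to every participant. The arms differ only in the metformin recommendation, so weight may fall in both arms whether or not the recommendation adds anything. A change within one arm mixes the DPP, the recommendation and any background trend. A change measured against an external untreated group estimates at best the whole package, without the protection of randomisation. The contrast that clinic randomisation supports is the difference between arms, and it is not written down.

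What is at stake is the pilot's usefulness. The Synopsis says the data will inform the design and power of a larger trial, and Section 3 describes that trial as testing the lifestyle programme combined with metformin. Its designers will want an estimate of the arm difference with an honest statement of its uncertainty. A report that follows Section 13 literally need not contain either.

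**Working it through.** **1. Inputs (Section 12).** Two clinics per arm; 25 patients per clinic (50 per arm), or 40 per arm after 20% attrition, which is 20 per clinic; ICC 0.01.

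**2. The plan's effective sizes.** D = 1 + ICC × (m − 1).
- m = 25: D = 1 + 0.01 × 24 = 1.24; 50 / 1.24 = 40.3.
- m = 20: D = 1 + 0.01 × 19 = 1.19; 40 / 1.19 = 33.6.

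These reproduce the stated 40 and 33.

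**3. The plan's interval widths.** The single-arm half-width in SD units is t(0.975, n − 1) / √n.
- n = 50: 0.284, matching ±0.28.
- n = 33.6: 0.351, matching ±0.35.

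Both are one-sample widths. The smallest possible between-arm half-width with these numbers is 1.96 × √(2/50) = 0.39 SD (50 per arm, ICC 0), already above the stated range. Section 12 therefore describes the precision of each arm's own change, which supports the per-arm reading of Section 13.

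A side point: ±0.28 comes from the nominal 50. The effective size of 40 quoted just before it gives 0.31 (normal) to 0.32 (t).

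**4. Width of the between-arm difference.** SE = √(2D/n) in SD units of the outcome, assuming equal SDs in the arms. The last column uses t(0.975, 2) = 4.303, where 4 clinics − 2 arms = 2 df. That is an assumption, because the plan names no degrees-of-freedom method. The ICC of 0.05 is also an assumption, included to show the range.

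| Patients per arm | ICC | D | SE | ± normal | ± t, 2 df |
|---|---|---|---|---|---|
| 50 | 0 | 1.00 | 0.200 | 0.39 | 0.86 |
| 50 | 0.01 | 1.24 | 0.223 | 0.44 | 0.96 |
| 40 | 0.01 | 1.19 | 0.244 | 0.48 | 1.05 |
| 40 | 0.05 | 1.95 | 0.312 | 0.61 | 1.34 |

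**5. Separating the two sources of width.** Going from one arm to a difference multiplies the half-width by √2: at ICC 0.01 with normal quantiles, 0.31 becomes 0.44 and 0.34 becomes 0.48. The rest comes from having four clinics and is not peculiar to the difference. With the same 2 df, the per-arm half-widths would themselves be 4.303 × √(1.24/50) = 0.68 and 4.303 × √(1.19/40) = 0.74 SD.

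**6. Whether the interaction wording fills the gap.** Weight is measured at baseline, 6 and 12 months. With visit as a category, a treatment-by-time test covers both follow-up visits jointly; with a linear trend, it compares slopes. Neither is the month-12 difference, and the phrase appears as a reason for caring about missing data, not as a specified analysis.

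**The case against.** The strongest reply is that this is a feasibility pilot. Section 3 gives feasibility as the primary aim, Section 12 ties sample size to feasibility and precision, and no alpha, power or decision rule is set. Arm-level changes with intervals can be a deliberate target, and the external control group gives them a stated use. The wording *by intervention* is also loose enough to include an arm-by-time model, which the interaction remark suggests was in mind. Month 12 is fixed as the outcome time elsewhere.

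Much of this stands. The absence of a powered test is not a fault, and the planned model can produce the arm difference. It would therefore go too far to infer that the analysis is incapable of answering the comparison. What does not stand is that the comparison is already specified: the single-arm precision, the external reference and the imputation target all point to per-arm estimates.

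A reader might also infer that the arms will be compared by whether only one interval excludes zero, or by whether the intervals overlap, and attach false-positive rates to those rules. The documents contain neither rule, so such rates would describe a possible misuse by readers and not a property of this plan.

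**Conclusion.** The point holds as a gap between the stated comparison and the stated estimates. Followed literally, Section 13 yields no month-12 estimate of what the metformin recommendation adds to the DPP.

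The missing estimate will be imprecise: about ±0.44 to ±0.48 SD at ICC 0.01 with normal quantiles, and about ±0.96 to ±1.05 SD with 2 df, against the ±0.28 to ±0.35 SD now quoted for a single arm. These widths assume equal SDs in the arms, equal clinic sizes and no gain from baseline adjustment. The choice of degrees of freedom matters more than the ICC over the range shown. The conclusion that the contrast is unnamed rests on the text and on the reproduction of Section 12's one-sample widths, not on these assumptions.

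**What to change.** In Section 13:

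- Name the between-arm difference (DPP-recommendations minus DPP) at month 12, in percent change in body weight and in HbA1c, as the estimate for the metformin-recommendation comparison. Take it from the same mixed model, with a 95% CI and a stated degrees-of-freedom method suited to four clinics.
- Label the per-arm changes, the external-control comparison, the month-6 contrast and the overall treatment-by-time test as descriptive or supportive.
- Have multiple imputation pool the same between-arm contrast.

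In Section 12, add the expected half-width of the between-arm difference beside the per-arm figures, and reconcile ±0.28 with the effective size of 40.

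The cost is a few sentences in two sections, with no new patients, visits or data. The downside is that the interval for the comparison is visibly wider than the one now quoted. The report should present it as an imprecise pilot estimate for planning, not as a test of the recommendation.
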